1.5 Risk/Benefit

Patients with CM, and particularly those with unresectable or metastatic CM following anti-PD-1/anti-PD-L1 antibody treatment represent populations with high unmet need. As discussed in Section 1.2, an estimated 30% to 70% of patients do not respond to initial anti-PD-1/anti-PD-L1 therapy and approximately 25% of patients eventually progress and may have no other therapeutic options. Therefore, there is an urgent need to identify new targeted therapies and/or combination therapies to overcome current IL-2 limitations that contribute to significant toxicity.

The available clinical data for ANV419 suggest ANV419 may have a favorable risk/benefit profile for patients with melanoma and this will be further explored in the ANV419-101 study.

The preclinical data demonstrate that ANV419 is a uniquely engineered "not- α " IL-2R agonist that signals preferentially through the intermediate affinity IL-2R β/γ and thus strongly stimulates proliferation of CD8+ T cells and NK cells while avoiding proliferation of immunosuppressive Tregs.

Since ANV419 is an experimental medicine, it is possible that unforeseen, unknown, or unanticipated drug reactions and toxicities may occur. However, as detailed below, this Protocol is designed to mitigate risks to patients through a detailed plan for careful safety monitoring, systemic review of AEs, SAEs, and active pharmacovigilance review to assess for safety signals or trends.

2 STUDY OBJECTIVES AND ENDPOINTS

The study objectives and endpoints for Part 1: Monotherapy Dose Expansion, Part 2: Combination Dose Finding, and Part 3: Combination Dose Expansion are provided in Table 2, Table 3, and Table 4.

Table 2. Study Objectives and Endpoints for Part 1: Monotherapy Dose Expansion

Part 1: Monotherapy Dose Expansion – Arms A1 and A2			
Primary Objectives	Primary Endpoints		
Evaluate the efficacy of ANV419	ORR (CR + PR), as defined by RECIST v1.1 (hereinafter, RECIST).		
Secondary Objectives	Secondary Endpoints		
To characterize the tumor	Secondary Endpoints		
response according to modified			
RECIST v1.1 criteria for			
immune-based therapeutics	Tumor response in terms of objective response rate (ORR: CR + PR)		
(iRECIST)	assessed by iRECIST		
	- DOR (per RECIST) and iDOR (per iRECIST[1]) measured from first		
	response until disease progression;		
	- DCR (DCR = $CR + PR + SD$), $iDCR$ ($iDCR = iCR + iPR + iSD$), PFS,		
	iPFS, and OS;		
Expand evaluation of efficacy of	- Median TTR; and		
ANV419	- Median iTTR.		
	Incidence, frequency, and severity of AEs including the following:		
	- SAEs;		
	- irAEs; - AESIs;		
	- AESIS, - AEs leading to discontinuation of the study; and		
	- Changes from baseline in laboratory parameters, vital signs, ECGs, and		
Evaluate the safety of ANV419	physical examination.		
Explore immunogenicity after	Silysical examination.		
exposure to ANV419	Incidence of immunogenicity as indicated by ADA.		
Exploratory Objectives	Exploratory Endpoints		
Exploratory objectives	Changes in immunological biomarker expression from baseline and post		
	treatment tumor and liquid biopsies, including:		
	- Immune cell counts, immunophenotyping (including, but not limited to,		
	CD3, CD4, CD8, CD56, CD16, CD25, FoxP3, CD279, and CD366);		
	- Cytokine production (including, but not limited to, IFNγ, IL-2, TNF, IL-		
	6, IL-10); and		
	- Immunohistochemistry (including, but not limited to, CD8, CD4, Ki67).		
	Analysis of mutations in the tumor and analysis of tumor mutational burden.		
	Analysis of changes in baseline ctDNA and at specified timepoints on		
Explore the changes in the tumor	therapy and after therapy.		
microenvironment before and	Analysis of single nucleotide polymorphisms, germline DNA for		
after adding ANV419 as	genome-wide association studies, analysis of T cell receptor repertoire,		
monotherapy	epigenetic markers, soluble CD25, and soluble PD-1/PD-L1.		


AE = adverse event; AESI = adverse event of special interest; CD = cluster of differentiation; CR = complete response; ctDNA = circulating tumor deoxyribonucleic acid; DCR = disease control rate; DOR = duration of response; ECG = electrocardiogram; FoxP3 = Forkhead box P3; iCR = immune complete response; iDCR = immune disease control rate; iDOR = immune duration of response; IFNγ = interferon gamma; IL = interleukin; iPFS = immune progression-free survival; iPR = immune partial response; irAE = immune related adverse event; iRECIST = immune Response Evaluation Criteria in Solid Tumors; iSD = immune stable disease; iTTR = immune time to response; ORR = objective response rate; OS = overall survival; PD-1 = programmed death-1; PD-L1 = programmed death-ligand 1; PFS = progression-free survival; PR = partial response; RECIST = Response Evaluation Criteria in Solid Tumors; SAE = serious adverse event; SD = stable disease; T cell = thymus lymphocyte cell; TNF = tumor necrosis factor; TTR = time to response; v1.1 = version 1.1.

Table 3. Study Objectives and Endpoints for Part 2: Combination Dose Finding

Table 3. Study Objectives and Endpoints for Part 2: Combination Dose Finding				
Combination Dose Finding – Combination Therapy Arms (Arms B and C)				
Primary Objectives	Primary Endpoints			
Evaluate the safety and tolerability and determine the RP2D of ANV419 in combination with pembrolizumab	Incidence, frequency, and severity of AEs including the following: - SAEs; - TEAEs; - DLTs;			
Evaluate the safety and tolerability and determine the RP2D of ANV419 in combination with ipilimumab	 AESIs; irAEs; AEs leading to discontinuation of the study; and Changes from baseline in laboratory parameters, vital signs, ECGs, and physical examinations. 			
Secondary Objectives	Secondary Endpoints			
Evaluate PK and PD of ANV419 in combination with	PK endpoints in serum: - CL of ANV419; - V _{ss} of ANV419; - AUC of ANV419; and - C _{max} of ANV419. PD endpoints in peripheral blood: including, but not limited to, CD3, CD4,			
pembrolizumab or ipilimumab	CD8, CD56, CD16, CD25, FoxP3, CD279, and CD366.			
Explore immunogenicity after exposure to ANV419 in combination with pembrolizumab or ipilimumab	Incidence of immunogenicity as indicated by ADA.			
Evaluate the efficacy of ANV419 in combination with pembrolizumab or ipilimumab	ORR (CR + PR), as defined by RECIST.			
Expand evaluation of efficacy of ANV419 in combination with pembrolizumab or ipilimumab	DOR (per RECIST) and iDOR (per iRECIST[1]) measured from first response until disease progression; PFS, iPFS, and OS; DCR (DCR = CR + PR + SD), iDCR (iDCR = iCR + iPR + iSD), Median TTR; and Median iTTR.			
Evaluate clinical benefit in quality of life after exposure to ANV419 in combination with pembrolizumab or ipilimumab	Change in QoL at baseline and every 12 weeks while receiving ANV419 via QoL evaluations: - EQ-5D-5L; and - QLQ-C30.			
Exploratory Objectives	Exploratory Endpoints			
Explore the changes in the tumor microenvironment before and after adding ANV419 as	 Changes in immunological biomarker expression from baseline and post treatment tumor and liquid biopsies, including: Immune cell counts, immunophenotyping (including, but not limited to, CD3, CD4, CD8, CD56, CD16, CD25, FoxP3, CD279, and CD366); Cytokine production (including, but not limited to, IFNγ, IL-2, TNF, IL-6, IL-10); and Immunohistochemistry (including, but not limited to, CD8, CD4, Ki67). 			
monotherapy and in combination	Analysis of mutations in the tumor and analysis of tumor mutational burden.			
with pembrolizumab or ipilimumab	Analysis of changes in baseline ctDNA and at specified timepoints on therapy and after therapy.			

Analysis of single nucleotide polymorphisms, germline DNA for
genome-wide association studies, analysis of T cell receptor repertoire,
epigenetic markers, soluble CD25, and soluble PD-1/PD-L1.

Table 3. Study Objectives and Endpoints for Part 2: Combination Dose Finding (Continued)

ADA = anti-drug antibodies; AE = adverse event; AESI = adverse event of special interest; AUC = area under the concentration-time curve; CD = cluster of differentiation; CL = systemic clearance; C_{max} = maximum observed serum concentration; CR = complete response; ctDNA = circulating tumor deoxyribonucleic acid; DLT = dose-limiting toxicity; ECG = electrocardiogram; EQ-5D-5L = Euro-QoL 5 dimension 5 level; FoxP3 = Forkhead box P3; IFN γ = interferon gamma; IL = interleukin; irAE = immune-related adverse event; ORR = objective response rate; PD = pharmacodynamic(s); PD-1 = programmed death-1; PD-L1 = programmed death-ligand 1; PK = pharmacokinetic(s); PR = partial response; QLQ-C30 = quality of life core 30; QoL = quality of life; RECIST = Response Evaluation Criteria in Solid Tumors; RP2D = recommended Phase 2 dose; SAE = serious adverse event; T cell = thymus lymphocyte cell; TEAE = treatment-emergent adverse event; TNF = tumor necrosis factor; V_{ss} = volume of distribution at steady state.

Table 4. Study Objectives and Endpoints for Part 3: Combination Dose Expansion

Table 4. Study Objectives and Endpoints for Part 3: Combination Dose Expansion				
	Dose Expansion – Combination Therapy Arms (Arms B and C)			
Primary Objectives	Primary Endpoints			
Evaluate the efficacy of ANV419				
in combination with				
pembrolizumab or ipilimumab	ORR (CR + PR), as defined by RECIST.			
Secondary Objectives	Secondary Endpoints			
	- DOR (per RECIST) and iDOR (per iRECIST[0]) measured from first			
	response until disease progression;			
	- DCR (DCR = $CR + PR + SD$), $iDCR$ ($iDCR = iCR + iPR + iSD$), PFS ,			
Expand evaluation of efficacy of	iPFS, and OS;			
ANV419 in combination with	- Median TTR; and			
pembrolizumab or ipilimumab	- Median iTTR.			
Part 3: Combination I	Oose Expansion – Combination Therapy Arms (Arms B and C)			
Secondary Objectives	Secondary Endpoints			
	Incidence, frequency, and severity of AEs including the following:			
	- SAEs;			
	- irAEs;			
	- AESIs;			
Evaluate the safety of ANV419 in	- AEs leading to discontinuation of the study; and			
combination with pembrolizumab	- Changes from baseline in laboratory parameters, vital signs, ECGs, and			
or ipilimumab	physical examination.			
Evaluate clinical benefit in	Change in QoL at baseline and every 12 weeks while receiving ANV419 via			
quality of life after exposure to	QoL evaluations:			
ANV419 in combination with	- EQ-5D-5L; and			
pembrolizumab or ipilimumab	- QLQ-C30.			
Explore immunogenicity after				
exposure to ANV419 in				
combination with pembrolizumab				
or ipilimumab	Incidence of immunogenicity as indicated by ADA.			
Exploratory Objectives	Exploratory Endpoints			
	Changes in immunological biomarker expression from baseline and post			
	treatment tumor and liquid biopsies, including:			
	- Immune cell counts, immunophenotyping (including, but not limited to,			
Explore the changes in the tumor	CD3, CD4, CD8, CD56, CD16, CD25, FoxP3, CD279, and CD366);			
microenvironment before and	- Cytokine production (including, but not limited to, IFNγ, IL-2, TNF, IL-			
after adding ANV419 in	6, IL-10); and			
combination with pembrolizumab	- Immunohistochemistry (including, but not limited to, CD8, CD4, Ki67).			
or ipilimumab	Analysis of mutations in the tumor and analysis of tumor mutational burden.			

Analysis of changes in baseline ctDNA and at specified timepoints on therapy and after therapy.
Analysis of single nucleotide polymorphisms, germline DNA for
genome-wide association studies, analysis of T cell receptor repertoire,
epigenetic markers, soluble CD25, and soluble PD-1/PD-L1.

Table 4. Study Objectives and Endpoints for Part 3: Combination Dose Expansion (Continued)

AE = adverse event; AESI = adverse event of special interest; CD = cluster of differentiation; CR = complete response; ctDNA = circulating tumor deoxyribonucleic acid; DCR = disease control rate; DOR = duration of response; ECG = electrocardiogram; EQ-5D-5L = Euro-QoL 5 dimension 5 level; FoxP3 = Forkhead box P3; iCR = immune complete response; iDCR = immune disease control rate; iDOR = immune duration of response; IFNγ = interferon gamma; IL = interleukin; iPFS = immune progression-free survival; iPR = immune partial response; irAE = immune-related adverse event; iRECIST = immune Response Evaluation Criteria in Solid Tumors; iSD = immune stable disease; iTTR = immune time to response; ORR = objective response rate; OS = overall survival; PD-1 = programmed death-1; PD-L1 = programmed death-ligand 1; PFS = progression-free survival; PR = partial response; QLQ-C30 = quality of life core 30; QoL = quality of life; RECIST = Response Evaluation Criteria in Solid Tumors; SAE = serious adverse event; SD = stable disease; T cell = thymus lymphocyte cell; TNF = tumor necrosis factor; TTR = time to response.

3 STUDY DESCRIPTION

3.1 Summary of Study Design

This is a multi-site, open-label, randomized, parallel arm, Phase 1/2 adaptive study to evaluate the efficacy and safety of ANV419 as a monotherapy and in combination with pembrolizumab or ipilimumab in patients aged 18 years or older with advanced CM who have previously been treated with at least 1 line of standard of care immunotherapy, including an anti-PD-1/anti-PD-L1 antibody.

The 4 following treatment arms will be included in this study:

- Arm A1:
- Arm A2:
- Arm B: in combination with pembrolizumab (Keytruda®); and
- Arm C: in combination with ipilimumab (Yervoy®).

There will be up to 3 separate parts in this study: Part 1: Monotherapy Dose Expansion with patients randomized to receive infusion of ANV419 (

If Part 1 is successful, Part 2: Combination Dose Finding with patients randomized to Arms B and C with infusion of ANV419 and finally, Part 3: Combination Dose Expansion with patients randomized to Arms B and C (see Figure 3). A total of up to 130 patients are planned to be enrolled in the study: a maximum of 30 patients in the Monotherapy Dose Expansion part, a maximum of 50 patients in the Combination Dose Finding part, and a maximum of 50 patients in the Combination Dose Expansion part and Combination Dose Expansion part will be stratified by BRAF mutation status.

In the Combination Dose Expansion part, the number of patients within each arm will be determined by pre-defined decision rules presented in Table 5.

[figure not shown]

Figure 3. Study Design

In the Combination Dose Finding part, patients will be manually randomized to Arm B or Arm C. In the Monotherapy Dose Expansion part and the Combination Dose Expansion part, patients will be randomized by IRT into Arms A1 or A2 and Arms B or C, respectively.

^{* =} If ANV419 monotherapy is successful, the combination portion will be initiated.

^{** =} Dose escalation increment is decided by the SRC until RP2D of ANV419 per arm is identified.

^{*** =} Arm not meeting pre-specified ORR criteria may be stopped early after Stage 1.

Ipi = ipilimumab; IRT = Interactive Response Technology; ORR = objective response rate; Pembro = pembrolizumab; R = randomization; RP2D = recommended Phase 2 dose; SRC = Safety Review Committee.

The study will also assess other clinical parameters including progression free survival (PFS) and will provide the opportunity to explore blood- and tumor based markers that may predict response to ANV419 as monotherapy or in combination with anti-PD-1 or anti CTLA-4 antibodies.

3.1.1 Part 1: Monotherapy Dose Expansion

The Monotherapy Dose Expansion part (Arms A1 and A2) will be a parallel group part with a Bayesian sequential monitoring analysis²⁸ and up to 15 patients per arm. This part will establish the efficacy and safety of ANV419 as monotherapy.

Two doses of ANV419 will be explored: based on data collected in the ongoing Phase 1 ANV419-001 study at a frequency of within the current Protocol in the absence of disease progression or unacceptable toxicity and in the absence of data from Arms A1 and A2 showing an unfavorable risk/benefit profile for patients on ANV419 monotherapy.

Decision making on whether to continue the study beyond the Monotherapy Dose Expansion part, and the total number of patients recruited to this part, will be based on Bayesian sequential monitoring. The study will be stopped at the end of this part in the case of an unfavorable risk/benefit profile for ANV419 monotherapy. This includes observing a total of 0 of 30 responses from the 2 monotherapy arms combined (a strong signal that ANV419 does not induce a response) and/or report of any safety issues that might stop the trial. There is 95% certainty that the true objective response rate (ORR) is greater than 10% if we observe any 1 of the following:

- 2 responses in 3 to 7 patients;
- 3 responses in 8 to 13 patients;
- 4 responses in 14 to 19 patients; or
- 5 responses in 20 to 27 patients.

Response (complete response [CR] or partial response [PR]) will be assessed locally at each disease evaluation.

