8.2 Statistical Methods

8.2.1 Sample Size Determination

Monotherapy Dose Expansion part

This part of the study will use Bayesian sequential monitoring. A maximum of 15 patients will be enrolled and treated at each dose level arm. Aland A2 monotherapy arms will be analyzed as independent experiments, and also overall, and the following assumptions are made:

- Nothing is known *a priori*: assume a uniform prior, ie, the true ORR could be any value between 0% and 100%;
- A true ORR <6% indicates treatment failure; and
- A true ORR >10% indicates treatment success.

With a maximum of 15 patients in an arm, if no responses were observed, then the estimated true ORR would be 5.9%, with 90% confidence interval (CI) (0.3%, 17.1%). This would be sufficient evidence to suggest that the treatment is unlikely to be successful. With a maximum of 30 patients overall, if no responses were observed, then the estimated true ORR would be 3.1%, with 90% CI (0.2%, 9.2%). This would be sufficient evidence to suggest that the treatment at either dose is unlikely to be successful.

There is 95% certainty that the true ORR is greater than 10% if any 1 of the following are observed:

- 2 responses in 3 to 7 patients;
- 3 responses in 8 to 13 patients;
- 4 responses in 14 to 19 patients; or

• 5 responses in 20 to 27 patients.

Combination Dose Finding part

The Combination Dose Finding part will employ BOIN²⁹ to find the MTD/RP2D of Arm B (ANV419 in combination with pembrolizumab) and Arm C (ANV419 in combination with ipilimumab). For each arm, the following assumptions have been predefined for the dose escalation:

- Target DLT rate of 25%;
- Maximum of 25 patients;
- Maximum of 9 patients treated at the same dose level; and
- Maximum of 5 dose levels defined in Table 5 to be tested.

Patients will be enrolled and treated in cohorts of 3 patients (at least). Up to 50 patients in total will be enrolled for the Combination Dose Finding part, with a minimum of 6 patients treated at RP2D.

Combination Dose Expansion part (efficacy analysis)

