## 5 CHANGES FROM PROTOCOL-SPECIFIED STATISTICAL ANALYSES

Considering the results of the part 1, with a total of 0 response observed from the 2 monotherapy arms the following analysis will not be performed:

- All analysis related to part 2 (combination dose finding) and part 3 (combination dose expansion) as trial stopped after part 1.
- iRECIST analysis in part 1 (monotherapy dose expansion): due to lack of repeated scans once PD by RECIST is assessed, most of the PDs by iRECIST remained unconfirmed and therefore survival endpoints per RECIST will not be analysed.

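### Part 1 success list: 5 responses in 27 patients gives 94.5% certainty, not 95%, and the pooled analysis has no entry for 28 to 30 patients

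*Protocol*

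**What the plan says.** Protocol 3.1.1 introduces the list with "There is 95% certainty that the true objective response rate (ORR) is greater than 10% if we observe any 1 of the following". The first row is "2 responses in 3 to 7 patients"; the second requires 3 responses for 8 to 13 patients, the third 4 responses for 14 to 19, and the last is "5 responses in 20 to 27 patients". The same four rows appear in six places: the Part 1 and sample size parts of the protocol synopsis, Protocol 3.1.1 and 8.2.1, and SAP 2.2.1.1 and 2.2.4.

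Protocol 8.2.1 supplies the model: a uniform prior on the ORR, and the statement "A true ORR >10% indicates treatment success". Each arm has at most 15 patients. The arms are to be analysed as "independent experiments, and also overall", and Protocol 3.1 allows "a maximum of 30 patients in the Monotherapy Dose Expansion part".

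Protocol 3.1.1 also says that Bayesian sequential monitoring will decide both whether the study goes beyond Part 1 and how many patients Part 1 recruits.

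**The concern.** An arm stops at 15 patients, so the last row can only serve the pooled analysis of both arms. Two things look wrong with it.

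- Each of the first three rows ends at the last sample size that still reaches 95%. The last row runs one patient further, to a result below 95%.
- The list ends at 27 although pooled accrual can reach 30. At full accrual the plan gives a failure rule (0 of 30) but no count that reaches 95%.

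The list is the only 95% success criterion stated for the Part 1 monitoring. As printed, it attaches 95% certainty to a result that does not have it. A reader who carried 5 responses forward to 30 patients would be acting on 91.7%.

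**Working it through.** **Inputs.** Uniform prior, Beta(1,1), and success bound of 10% (Protocol 8.2.1); required certainty 95% and the four rows (Protocol 3.1.1); maximum 15 per arm (Protocol 8.2.1) and 30 overall (Protocol 3.1 and 8.2.1).

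**Formula.** With x responses in n patients the posterior is Beta(1+x, 1+n−x), so

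P(ORR > 0.10) = 1 − F(0.10; 1+x, 1+n−x) = P(Bin(n+1, 0.10) ≤ x),

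where F is the Beta distribution function.

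**Step 1: reproduce the plan's own figures.** For 0 of 15 the posterior is Beta(1,16). Its mean is 1/17 = 5.9% and its 5th and 95th percentiles are 0.32% and 17.07%. For 0 of 30 it is Beta(1,31), with mean 1/32 = 3.1% and percentiles 0.17% and 9.21%. Both agree with Protocol 8.2.1 (5.9%, 0.3% to 17.1%; 3.1%, 0.2% to 9.2%), so the model is the one the plan used.

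**Step 2: check each row at its ends and at the next n.**

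| Responses | Listed n | At first n | At last listed n | At next n |
|---|---|---|---|---|
| 2 | 3–7 | 99.63% | 96.19% | 94.70% (n=8) |
| 3 | 8–13 | 99.17% | 95.59% | 94.44% (n=14) |
| 4 | 14–19 | 98.73% | 95.68% | 94.8% (n=20) |
| 5 | 20–27 | 98.56% | **94.50%** | 93.63% (n=28) |

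The certainty falls as n rises within a row. Rows 1 to 3 therefore hold throughout and stop where they should. In row 4:

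- 5 of 26: P(Bin(27, 0.10) ≤ 5) = 0.95294
- 5 of 27: P(Bin(28, 0.10) ≤ 5) = 0.94499

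Of the 25 sample sizes from 3 to 27, 24 are right and n=27 is not.

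**Step 3: can rounding or another method explain 27?** To a whole percent, 0.94499 rounds to 94%. Relaxing the cut to 94.5% would extend row 1 to 8 and row 3 to 20, which the list does not do, and would still leave row 4 at 26. The largest n with 5 responses at 95% under other methods is 24 (Jeffreys prior), 21 (Haldane, Beta(0.1, 0.9) or Beta(0.2, 1.8)) and 20 (one-sided exact binomial test at 5%). None gives 27, and of these methods only the uniform prior reproduces rows 1 to 3.

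**Step 4: the pooled analysis from 27 to 30.**

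| n | 5 responses | 6 responses |
|---|---|---|
| 27 | 94.50% | 98.21% |
| 28 | 93.63% | 97.84% |
| 29 | 92.68% | 97.42% |
| 30 | 91.66% | 96.94% |

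The smallest count reaching 95% is 6 at each of these sample sizes. Six responses suffice up to n=33, so one added row covers the rest of Part 1.

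**Step 5: single arms.** At 15 patients the third row applies, and 4 of 15 gives 98.30%. No per-arm threshold is affected.

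**The case against.** The case against giving this weight has four parts.

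1. The list states conditions that are sufficient for 95% certainty. It does not claim to cover every sample size, so silence at 28 to 30 makes no printed statement false, and the missing count can be derived from the prior and the bound. This is right as far as it goes: the gap is an omission, whereas the entry at 27 is an error. A monitoring list for a pooled analysis of up to 30 patients should still reach 30.
2. The trigger for Part 2 is at least 2 responses in Part 1 (Protocol 3.1.2, SAP 2.2.1.2), not this list. A trial with 5 responses in 27 has already passed it. The SAP reports the primary endpoint with an exact Clopper-Pearson interval (3.4.3) and plans no formal hypothesis testing (3.1.4). This stands and limits the practical effect. It does not make the stated probability correct, and Protocol 3.1.1 does give the Bayesian monitoring a role in continuation and in Part 1 size.
3. The trial stopped after Part 1, "with a total of 0 response observed from the 2 monotherapy arms" (SAP section 5). This also stands: nothing in this trial's results depends on the row.
4. Four of the six corrections are in the protocol, where Protocol 11.1 puts every amendment through full review. That is a fair point about the route for the correction, not about whether it is needed.

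**Conclusion.** The last row is wrong as written at n=27, where 5 responses give 94.50% against the stated 95%, and the pooled analysis has no success count for 28 to 30 patients. The result rests on the plan's own uniform prior and 10% bound, and on reading 95% as a strict cut, which is how the first three rows apply it. The size is small: one sample size, 0.5 percentage points, pooled analysis only. With no responses observed, no conclusion of this trial changes. The list should still be corrected, because it is an incorrect threshold for the primary endpoint that stands in six places.

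**What to change.** End the last row at 26 patients (5 responses for 20 to 26) and add a row of 6 responses for 27 to 30. Make the change in the protocol synopsis (Part 1 and sample size), Protocol 3.1.1 and 8.2.1, and SAP 2.2.1.1 and 2.2.4.

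The change is to wording only. The pooled threshold at 27 rises from 5 to 6, and 28 to 30 gain a threshold. No other row, sample size or per-arm rule moves. If reopening the protocol of a stopped trial is judged out of proportion, correct the two SAP places and note the error in the clinical study report, so that the list is not carried uncorrected into a later protocol.
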